8.8. Host Genetics

A mandatory sample for HLA haplotyping will be collected from all participants.

An optional pharmacogenomic (host DNA) blood sample may be collected (preferably at baseline) to allow for host pharmacogenomic research, where local regulations permit. In addition, host DNA blood samples to allow for epigenetic analyses will be collected. These samples could for example be used to assess changes in frequencies of immune cells such as MDSCs. Complete host genomic testing may be done to search for links of specific genes to (HBV-related) liver disease or to the PK, PD, efficacy, safety, or tolerability of the study intervention. These samples will only be collected from participants who consent separately to this component of the study. Further, a participant may withdraw such consent at any time without affecting their participation in other aspects of the study, or their future participation in the Platform study (see Section 7.2.1 of the Master Protocol PLATFORMPAHPB2001).

In addition, other samples may be used for exploratory genetic or epigenetic research in participants consenting separately to this part of the study. No genetic research will be performed on any sample in participants who have not provided the additional separate consent for host genetic research. These samples can only be used to investigate the potential association of genetic or epigenetic factors with efficacy, safety, or PK of the study intervention, or HBV infection, or may be used to develop tests/assays related to the study intervention or HBV infection.

These analyses will be performed at the sponsor's discretion, will always be under the sponsor's supervision, and may be reported separately.

8.9. Exploratory Host Biomarkers

The study includes collection of blood samples for exploratory analysis of host blood biomarkers at the host RNA, protein, and cell level. Sampling will be performed at the time points indicated in the [Schedule of Activities](#). Leftovers of other samples might also be used for exploratory research of host and viral markers.

The analyses may include gene expression and cytokine analyses assessing markers such as interferon-stimulated genes (ISGs), IFN- α , and interferon γ -induced protein 10 (IP-10).

Samples can only be used for research related to study intervention or HBV infection or may be used to develop tests/assays related to study intervention or HBV infection.

Blood samples will be taken at the time points indicated in the [Schedule of Activities](#) which can be used to explore immunogenicity of JNJ-3989 and optionally PegIFN- α 2a. The emergence of antidrug antibodies to JNJ-3989 and optionally to PegIFN- α 2a might be analyzed using assays such as an enzyme-linked immunosorbent assay or functional assays.

These analyses will be performed at the sponsor's discretion, will always be under the sponsor's supervision, and may be reported separately.

More information is provided in Section 8.8 of the Master Protocol PLATFORMPAHPB2001.

9. STATISTICAL CONSIDERATIONS

Statistical analysis will be done by the sponsor or under the authority of the sponsor. A general description of the statistical methods to be used to analyze the efficacy and safety data is outlined below. Specific details will be provided in the Statistical Analysis Plan (SAP).

9.1. Statistical Hypotheses

As this is an exploratory single-arm study, no formal statistical hypothesis has been formulated.

9.2. Sample Size Determination

No formal sample size calculation was performed, as this is a single-arm study for exploratory and proof of concept (PoC) purposes. However, with a sample size of 50 participants having data for the primary efficacy endpoint at Week 24, if at least 25 (50%) participants are responders, it can be concluded with 90% confidence that the true response rate is at least 0.38, with a confidence interval (CI) width of 0.248 (90% CI: 0.376-0.624). With a sample size of 20 participants (for one of the IAs), the precision of the estimate of the primary efficacy endpoint decreases, as the two-sided 90% CI width increases. For the same assumed proportion of responders of 50% (10 out of 20 participants), the 90% CI width becomes 0.396. [Table 4](#) shows the 90% CI and the corresponding width for proportion of responders of 0.30, 0.50, 0.70, and 0.90.

Table 4: Sample Size Determination

Proportion of responders	N=20		N=50	
	90% CI*	Width of CI	90% CI*	Width of CI
0.30	0.140-0.508	0.368	0.195-0.424	0.229
0.50	0.302-0.698	0.396	0.376-0.624	0.248
0.70	0.492-0.860	0.368	0.576-0.805	0.229
0.90	0.717-0.982	0.265	0.801-0.960	0.159

CI: confidence interval.

* Clopper-Pearson exact method is used.

9.3. Populations for Analysis Sets

For purposes of analysis, the following populations are defined:

Population	Description
Screened	All participants who signed the ICF for the Master Protocol and an ICF specific for this ISA.
Enrolled	All participants who were enrolled in this ISA.
Intent-to-treat (ITT)	All participants who were enrolled and who received at least 1 dose of study intervention within this ISA.
IFN-ITT	All participants who were enrolled and who received at least 1 dose of PegIFN- α 2a within this ISA.

9.4. Statistical Analyses

The SAP will include a more technical and detailed description of the statistical analyses described in this section. This section is a summary of the planned statistical analyses of the most important endpoints including primary and key secondary endpoints.

9.4.1. General Considerations

Refer to Section 9.4.1 of the Master Protocol PLATFORMPAHPB2001.

9.4.2. Efficacy Analyses

The primary efficacy analysis will be performed when all participants have completed Week 24 (EOSI) or discontinued earlier. The final analysis will be performed when all participants have completed the last study visit (FU Week 48) or discontinued earlier.

To evaluate the efficacy, the primary analysis set will be the ITT population (defined in Section 9.3, Populations for Analysis Sets). Selected efficacy analyses will be repeated for the IFN-ITT analysis set and described in the SAP.

All efficacy summaries will be presented with descriptive statistics and 90% CIs. If the endpoint is continuous, the descriptive statistics will include the number of participants, mean, standard deviation (SD), median, and range. If the endpoint is binary or categorical, the frequency distribution with the number and percentage of participants in each category will be calculated. For time-to-event variables, a summary table including number of participants included in the analysis, number of participants censored, 25th and 75th percentiles and median time-to-event will be shown. Graphic displays will also be used to summarize the data.

The baseline measurements are defined as the measurements taken closest to but before the first administration of study intervention on Day 1, unless otherwise specified.

Additional analyses of efficacy to generate new hypotheses and guide the design of new studies may be performed on the primary efficacy endpoint and/or selected secondary endpoints using, for example, the Bayesian methodology or other methodologies to leverage the Platform Study framework. Such analyses may incorporate external data and/or data from other ISAs which are currently in the platform study or may enter in the future. Details on these analyses will be provided in a separate document (SAP or Modeling and Simulation Report, as applicable).

9.4.2.1. Primary Efficacy Endpoint

The primary endpoint is the proportion of participants with a reduction of at least 2 log₁₀ IU/mL in HBsAg levels from baseline to Week 24. Participants who do not have HBsAg data in the analysis window of Week 24 will be defined as non-responders.

The primary efficacy endpoint will be summarized with the point estimate paired with its 90% CI using the Clopper-Pearson exact method. The same method will apply in a secondary analysis of the primary endpoint to the IFN-ITT analysis set comprising the ITT participants who have received at least 1 dose of PegIFN- α 2a (see Section 9.3, Populations for Analysis Sets).

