9.5. Interim Analyses

Interim analyses (IAs) will be conducted to assess safety and efficacy to support the sponsor's interactions with health authorities, as well as to inform internal decisions about additional studies and/or investigation of other treatment combinations. The IAs are planned when:

- Approximately 20 participants have completed Week 24 (EOSI) or discontinued earlier
- All participants have completed Week 36 (FU Week 12) or discontinued earlier
- All participants have completed Week 48 (FU Week 24) or discontinued earlier.

An optional IA may be conducted when all participants have completed Week 60 (FU Week 36) or discontinued earlier.

The study is open-label, and the sponsor will conduct the pre-planned IAs. Hence, the study team and the DRC will have access to the IA results, while the investigators and participants will not.

Both primary and interim analyses will be based on all data available at the pre-defined cut-off time points, and may include data at later time points for those participants who have reached subsequent visits.

More details are provided in Section 9.5 of the Master Protocol PLATFORMPAHPB2001.

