5.3.2.1. Missing Data Handling Rule

The missing as non-responder is the primary rule to handle missing data. Two sensitivity analyses will be conducted using the observed case data and LOCF approach, respectively.

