5.3.2.1.2. Observed Case Analysis

Only participants who have HBsAg data at Week 24 will be used for the analysis.

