5.4.2.1.3. HBsAg Seroclearance

5.4.2.1.3.1. On Treatment

The count and proportion of participants (and associated 90% CI) who achieve HBsAg seroclearance over time during the study intervention phase will be summarized.

5.4.2.1.3.2. Off Treatment

The count and proportion of participants (and associated 90% CI) who achieve HBsAg seroclearance over time during FU will be summarized. Separate analyses will be performed for participants who completed treatment as planned (at the end of treatment period 2), and regardless when treatment was stopped.

The count and proportion of participants who achieve HBsAg seroclearance will be evaluated at each of the following off-treatment time points: 12, 24, 36 and 48 weeks, respectively, after stopping all study interventions and without restarting NA treatment. In an additional summary, these proportions will be calculated with the denominator including only those participants who have reached the off-treatment timepoint (week 12, 24, 36 or 48), and have stopped all interventions including NA and have not restarted NA prior to the timepoint of interest.

For all time points, HBsAg seroclearance will be analyzed using the observed case data. LOCF will be used for selected time points (Section 5.4.2.1.1).

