5.4.2.1.4. Functional Cure

The count and proportion of participants (and associated 90% CI) who achieve FC at each of the selected FU time points will be summarized descriptively.

The main analysis will be on observed cases data with no imputation of missing values.

Two sensitivity analyses will be performed.

1. Missing as non-response: If participants withdrew from the study prior to the selected FU time point or had missing HBsAg values at the selected FU time point, they will be considered as non-responders.
2. LOCF: If participants withdrew from the study prior to the selected FU time point, they will be considered as non-responders. The LOCF rules to handle missing data will be applied to selected time points as explained in Section 5.4.2.1.1.

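### At the first interim analysis, counting the first 20 or so participants to complete Week 24 or drop out over-represents dropouts and biases the response rate downward

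*Protocol*

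**What the plan says.** - **Trigger.** Protocol 9.5 and SAP 5.8.3.2 start IA1 when "Approximately 20 participants have completed Week 24 (EOSI) or discontinued earlier".
- **Data used.** Protocol 9.5 adds: "Both primary and interim analyses will be based on all data available at the pre-defined cut-off time points". SAP 5.8.3.2 says the same.
- **Analysis set.** The primary efficacy set (ITT in Protocol 9.3, FAS in the SAP) is "All participants who were enrolled and who received at least 1 dose of study intervention within this ISA". It carries no condition on having reached Week 24, and no separate set is defined for an interim.
- **Missing data.** Protocol 9.4.2.1 and SAP 5.3.2.1.1 state: "Participants who do not have HBsAg data in the analysis window of Week 24 will be defined as non-responders". SAP 5.3.2.1 confirms the status of this rule: "The missing as non-responder is the primary rule to handle missing data". An observed-case analysis and a modified LOCF are sensitivity analyses.
- **Stated size of IA1.** Protocol 9.2 and SAP Section 3 give precision for 10 responders out of 20. SAP Table 10 labels IA1 as N=20 and the primary analysis as N=50.

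**The concern.** The missing-data rule suits the primary analysis, which waits until everyone has completed Week 24 or discontinued (Protocol 9.4.2). IA1 is different, because part of the trial is still on treatment when it is run.

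A completer becomes countable 24 weeks after first dose. A dropout becomes countable on the day of dropping out, which can be much sooner. If the IA1 set is whoever has completed or discontinued by the cut-off, dropouts come from recent as well as early enrolment, and completers from early enrolment only. Since dropouts without a Week 24 value are failures, the response rate is pulled down.

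The text leaves a second gap. Nothing in the FAS definition or the missing-data rule exempts a dosed participant whose Week 24 visit is not yet due.

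Protocol 9.5 gives the interims two uses: interactions with health authorities, and internal decisions on further studies and combinations. A rate that is low because of how the set was formed could mislead either one.

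**Working it through.** **1. The plan's own figure.** The two-sided 90% Clopper-Pearson limits are the 0.05 quantile of Beta(x, n−x+1) and the 0.95 quantile of Beta(x+1, n−x). For 10/20 they are 0.302 and 0.698, width 0.396, as in Protocol Table 4. All eight intervals in that table reproduce to three decimals.

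**2. Inputs for the trigger effect.** From the documents: 50 participants, IA1 at the 20th to complete or discontinue, a 24-week treatment period, missing counted as non-response. The rest is assumed, because the documents give no accrual, dropout or response rate:
- even accrual over 12, 26, 40 or 52 weeks;
- dropout probability d of 5%, 10% or 20%, timed evenly over 24 weeks;
- 60% response in completers;
- no Week 24 HBsAg value for dropouts.

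**3. Target and bias.** The rate to be estimated is 0.60 × (1 − d): 57.0%, 54.0% and 48.0%. If s is the share of dropouts among the 20 analysed, the expected IA1 rate is 0.60 × (1 − s), so the bias is 0.60 × (s − d).

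**4. Simulation** (20,000 runs per cell). Each cell shows the mean IA1 rate, with the shortfall in percentage points and s in brackets.

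| Accrual | d = 5% (target 57.0%) | d = 10% (target 54.0%) | d = 20% (target 48.0%) |
|---|---|---|---|
| 12 weeks | 53.1% (3.9; 11.3%) | 46.5% (7.5; 22.3%) | 33.8% (14.2; 43.5%) |
| 26 weeks | 54.1% (2.9; 9.8%) | 48.4% (5.6; 19.3%) | 37.7% (10.3; 37.1%) |
| 40 weeks | 55.0% (2.0; 8.5%) | 50.1% (3.9; 16.6%) | 40.8% (7.2; 32.0%) |
| 52 weeks | 55.3% (1.7; 7.8%) | 50.9% (3.1; 15.2%) | 42.4% (5.6; 29.2%) |

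Check on one cell (26 weeks, 10%): 0.60 × (0.193 − 0.100) = 0.056, which matches.

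The 12-week, 10% cell shows the mechanism. The whole trial expects 50 × 0.10 = 5 dropouts and 45 completers. The IA1 set holds about 20 × 0.223 = 4.5 of the dropouts but only 15.5 of the completers.

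**5. A different response assumption.** Setting the overall rate at 50% instead of 60% in completers, with accrual over 12, 26 or 52 weeks, gives IA1 rates of 46.7% to 48.6% at 5% dropout, 43.1% to 47.2% at 10% and 35.4% to 44.2% at 20%. The bias is again downward throughout and of similar size.

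**6. Dosing order instead.** Taking the first 20 dosed and waiting for all of them to pass Week 24, the simulated rate is within 0.2 points of target in every cell.

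**7. The sensitivity analyses.** The observed-case analysis states: "Only participants who have HBsAg data at Week 24 will be used for the analysis". That removes participants not yet due, but also every dropout without a Week 24 value. In the simulation it returns about 60% whatever the dropout rate, which is the completer rate and not the primary quantity. The LOCF version (SAP 5.3.2.1.3) scores anyone without a value within 4 weeks of Week 24 as a non-responder, so it does not repair the set either.

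**The case against.** **The stated N.** A reader might infer that IA1 scores every dosed participant not yet due at Week 24 as a failure. With 10 responders among 20 resolved participants, that reading would give 10/30 = 33.3% (90% CI 19.3 to 49.9), 10/40 = 25.0% (14.2 to 38.7) or 10/50 = 20.0% (11.3 to 31.6) for 30, 40 or 50 dosed. The literal text permits it, but Protocol 9.2, SAP Section 3 and SAP Table 10 all put IA1 at 20, and a visit not yet due is not ordinarily called missing. These figures therefore show what the wording leaves open, not what is planned. The objection succeeds against that reading. It does not settle which 20 are meant.

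**Size and consequence.** At 10% dropout and 40-week accrual the bias is 3.9 points, against a 90% CI half-width of 0.396/2, about 20 points, at N=20. There is no hypothesis and no formal test, neither document gives an IA1 stopping rule, and the N=50 analysis follows. All of this stands and limits the matter to a misleading interim estimate. A known one-directional bias is still worth removing when removal is nearly free.

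**Functional and partial cure.** A reader might extend the point to these endpoints, where participants who withdrew or "had missing HBsAg values at the selected FU time point, they will be considered as non-responders". The documents do not support this. That rule is only a sensitivity analysis there, with observed cases as the main analysis (SAP 5.4.2.1.4 and 5.4.2.1.13). The later interims wait for all participants at their target visits.

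**Text not seen.** Protocol 9.5 refers to Master Protocol 9.5 for more detail, and 9.4.1 refers to its general considerations. An IA1 set may be defined there. The gap is established only for this protocol and SAP.

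**Conclusion.** The point holds, and the change should be made. As triggered, with the 20 taken as the first to complete or discontinue, IA1 gives a response rate that is biased downward. Under the assumptions listed, the bias is about 2 to 4 points at 5% dropout, 3 to 8 at 10% and 6 to 14 at 20%, and it is larger with faster accrual. The direction was the same in every scenario. The size depends on dropout and accrual rates that the documents do not give. The missing-data rule itself is sound, and the primary analysis is unaffected. The fault lies in the undefined IA1 set.

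**What to change.** In Protocol 9.5 and SAP 5.8.3.2, with a cross-reference in SAP 5.3.2.1.1, define the IA1 set for the primary endpoint by dosing order. It would be the first approximately 20 participants dosed, analysed once all of them have passed the end of the Week 24 window (day 183 from first dose in SAP Table 4), whether or not they discontinued. Apply missing-equals-non-responder only within that set. This settles both which 20 are meant and how participants not yet due are handled.

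The SAP already uses a similar device in an additional summary of off-treatment seroclearance, where "these proportions will be calculated with the denominator including only those participants who have reached the off-treatment timepoint".

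Keep the rule to the primary endpoint. Follow-up windows run from the start of follow-up and the FU Week 48 window is open-ended (SAP 5.1.2.3 and Table 4), so a cut-off counted from first dose does not carry over to follow-up endpoints.

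The cost is a few sentences and one date-derived flag, with no extra data. IA1 would come somewhat later: about 2.5 to 4.6 weeks in the simulation, of which (183 − 168)/7 = 2.1 weeks is waiting for the window to close.

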9.4.2.2. Secondary Efficacy Endpoints

Descriptive statistics and 90% CIs will be used to summarize all efficacy endpoints.

Specific key selected endpoints may be analyzed using suitable categorical data approaches (eg, Clopper-Pearson interval or logistic regression for proportions or other categorical type of endpoint), longitudinal repeated measures models (eg, for continuous types of variables), or survival analysis based on the Kaplan-Meier estimates (for time-to-event variables), as appropriate.

9.4.2.3. Resistance Analyses

The results of HBV viral sequencing will be evaluated by the sponsor virologist. Relevant changes of amino acid and/or nucleic acid variations (eg, substitutions) in the HBV genome will be tabulated and described.

Additional exploratory characterization of the HBV viral sequence and phenotype may be performed and reported separately.

9.4.3. Safety Analyses

Safety analyses are specified in Section 9.4.3 of the Master protocol PLATFORMPAHPB2001.

Safety will be evaluated by means of descriptive summaries of (S)AEs including AEs of special interest to any of the study interventions, clinical laboratory tests, ECGs, vital signs, and physical examinations. The safety analysis will be done by study period. Results will be presented in tabular format and/or graphically over time, as appropriate.

9.4.4. Other Analyses

Pharmacokinetic Analyses

Descriptive statistics (n, mean, SD, coefficient of variation [CV], geometric mean, median, minimum, and maximum) will be calculated for the plasma concentrations of JNJ-3989 (JNJ-3976, and JNJ-3924) and, optionally, of NA, PegIFN- α 2a and/or JNJ-6379, and for the derived plasma PK parameters for noncompartmental PK analyses.

For each participant with intensive PK sampling, plasma concentration-time data of JNJ-3976 and JNJ-3924, and, optionally, of NA, PegIFN- α 2a and/or JNJ-6379, will be graphically presented. Similarly, graphs of the mean plasma concentration-time profiles and overlay graphs with combined individual plasma concentration-time profiles will be produced. Plasma PK parameters in participants undergoing intensive PK sampling will be calculated via noncompartmental methods for JNJ-3976 and JNJ-3924, and, optionally, NA, PegIFN- α 2a and/or JNJ-6379. The PK parameters will be C_{max} , C_{24h} , and AUC_{24h} ; other PK parameters may also be calculated. The PK parameters will be subjected to an exploratory graphical analysis, including various transformations, to get a general overview.

To assess the effect of PegIFN- α 2a on JNJ-6379 (as applicable) and JNJ-3989, the PK parameters of JNJ-6379 (as applicable) and JNJ-3989 coadministered with PegIFN- α 2a at Week 20 (or 16) will be compared to those of JNJ-6379 (as applicable) and JNJ-3989 at Week 4 (or 8) as reference. The primary PK parameters are C_{max} and AUC_{24h} on the logarithmic scale. A mixed effects model will be fitted to log-transformed PK parameters with treatment period as a fixed effect and participant as a random effect.

Special attention will be paid to the plasma concentrations and PK parameters of those participants who discontinued the study for an AE, or who experienced an AE \geq grade 3, or an SAE.

Population PK analysis of plasma concentration-time data of JNJ-3976 and JNJ-3924 may be performed using non-linear mixed effects modeling. Data may be combined with those from Phase 1 and/or 2 studies to support a relevant structural model. Available baseline characteristics (eg, demographics, laboratory variables, genotypes) may be included in the model as necessary. If a population PK analysis is conducted, the results will be presented either in the clinical study report or in a separate report.

Pharmacokinetic/Pharmacodynamic Analyses

Relationships of PK parameters for JNJ-3976 and JNJ-3924, and, optionally, of NA, PegIFN- α 2a and/or JNJ-6379 with selected efficacy and/or safety endpoints may be evaluated and graphically displayed.

Modeling of key PD parameters (eg, HBsAg, HBV DNA) may be performed using population PK/PD. If PK/PD modeling of key efficacy endpoints is performed, treatment effect and possible covariates may be investigated. Other biomarkers may be explored at the sponsor's discretion. If conducted, the results will be presented in a separate report.

Immune Analyses

Descriptive statistics (n, mean, SD, CV, geometric mean, median, minimum, and maximum) will be used to describe the magnitude of the IFN- γ T-cell response or the CD4+ and CD8+ T-cell responses (expressing at least 1 cytokine such as IL-2, TNF- α or IFN- γ specific to any HBV antigen) as defined by ELISpot and/or ICS, respectively. Changes from baseline (if present) will also be tabulated for PBMCs during study intervention and follow-up. The proportion (%) of CHB patients with positive responses based on the magnitude of the IFN- γ T-cell response or the CD4+

or CD8+ T-cells expressing at least 1 of the cytokines amongst IL-2, TNF- α or IFN- γ for 1 of the HBV antigens as defined by ELISpot and/or ICS, respectively, will be determined. Other immune cells, such as NK-cells, MDSCs, DCs, and B-cells, may be evaluated/explored.

Pharmacogenomic Analyses

The statistical approach for analyzing the exploratory host DNA research, including epigenetic analyses, may depend on the objective of the analyses (eg, efficacy, safety, and/or PK) and possibly relevant genes at the time of analysis. Analyses will be conducted at the sponsor's discretion, will always be under the sponsor's supervision, and results will be presented either in the clinical study report or a separate report.

Host Biomarker Analyses

Statistical approaches to explore correlations between clinical outcome and blood biomarkers vary and depend on the different data types of the applied technology platforms, as well as on the extent of observed interindividual variability. Analyses will be conducted at the sponsor's discretion, will always be under the sponsor's supervision, and results will be presented either in the clinical study report or a separate report.

